FENUGREEK: AN EMERGENT ALLERGEN

NCT ID not yet assigned

DATE: January 15, 2024

Introduction

Fenugreek or *Trigonella foenum greacum* is an ancient medicinal plant native to the eastern Mediterranean; it belongs to Rosaceae order, Leguminosae family, subfamily of Papilonaceae and it is used as a medicinal herb, spice or food.

Fenugreek is a short-lived annual angiosperm plant, 50 cm tall; it has green trifoliate leaves, white or yellow flowers and thin, curved pods containing about 10-20 golden yellow seeds. Its name comes from the triangular shape of its flowers (from Latin "trigonum").

Fenugreek seeds are ground and the powder is used as a condiment or in traditional Ayurvedic and Chinese medicine.

It is used in Indian cuisine as a component of spice mix, such as curry, instead in Egypt it is also used as a supplement in wheat and corn flour for bread-making. Fenugreek appears to have many health benefits and potential medicinal properties (antioxidant, antidiabetic, hepatoprotective, hypcholesterolemic, antimicrobial, anti- inflammatory, neuroprotective, anticarcinogenic, antiulcer, and antilithogenic) both in vitro and in vivo studies (Ouzir et al., 2016; Neelakantan et al., 2014; Yadav et al., 2014; Nagulapalli Venkata et al., 2017).

Fenugreek seed contains: soluble galactomannan, insoluble fiber, proteins, lipids, alkaloids (trigonelline), saponins (based on diosgenin and yamogenin), 4-hydroxyisoleu-cin, volatile oil and C-glycosylflavones of apigenin and luteolin (Yao et al., 2020).

Specifically, it is mainly used to improve digestion, activate metabolism, facilitate delivery, and increase milk flow. Trigonelline appears to be the most active metabolite in fenugreek; it is useful in treating diabetes, reducing cholesterolemia, and treating cancers (liver, breast, cervix, and pancreas) as a phytohormone (Bahmani et al., 2016; Smith et al., 2003).

In addition, fenugreek is used as a cut/crushed seed, herbal preparation, dry extract, soft extract, powder, or in combination with other substances; its main applications are appetite enhancement, topical treatment of localized inflammation of the skin and gut, as an adjuvant in diabetes or hypercholesterolemia.

It is non-toxic up to the maximum dose of 5 g/kg weight. Side effects such as flatulence, diarrhea, abdominal distension, dyspepsia, hypokalemia, increased frequency of urination, and dizziness have been reported.

Among immunologic adverse reactions, the literature reports mainly allergic reactions after contact or ingestion of fenugreek, characterized by urticaria, angioedema, dyspnea, cough, rhinorrhea, and

itching. Type IV or delayed skin reactions following contact with fenugreek preparations are rare but possible. Finally, many authors report the known cross-reactivity between fenugreek and foods belonging to the legume (or Fabaceae) family (European Medicines Agency Assessment Report on *Trigonella Foenum-Graecum L.*, Semen; 2018; Minciullo et al., 2017; Che et al., 2017; Vinje et al., 2012).

Purpose of the study

Given that the use of fenugreek is increasing worldwide, both in diet and nutraceuticals, we can expect an increase in adverse reactions in the coming years.

The purpose of this study is to analyze the medical history of patients who came to our operating unit for suspected adverse reactions after ingestion of fenugreek and to highlight possible cross-reactivity between fenugreek and other legumes or other foods.

Study design

Type of the study

The proposed study is observational, spontaneous, retrospective.

Study location

The study will be carried out at the A.O.U. "G. Martino" of Messina, Operative Unit of Allergy and Clinical Immunology.

Possible benefits

To assess the true incidence of sensitization to fenugreek in the population with clinical history indicative of allergy to spices or nutraceuticals containing this substance, since fenugreek is increasingly used both in food preparation and for therapeutic purposes. The finding of relevant allergenicity of fenugreek could prompt further study of molecular allergens useful for highlighting new patterns of cross-reactivity.

Possible adverse effects

None.

Clinical Case History.

As this is a retrospective study, the clinical case series consists of patients with history suggestive of allergic reaction to foods probably containing fenugreek, who are referred to the Operative Unit of Allergy and Clinical Immunology of the A.O.U. "G. Martino" of Messina on an outpatient visit during the period from January 2022 to December 2023 to perform skin prick tests for foods.

Inclusion criteria.

All patients over the age of 18 years, who came to the outpatient clinic of the Operative Unit of Allergy and Clinical Immunology for suspected allergic reaction after ingestion of spicy foods or intake of phytotherapeutic products containing fenugreek and were prick-by-prick tested with fenugreek, will be included.

Exclusion criteria.

All patients younger than 18 years of age and patients who came to the outpatient clinic of the Operative Unit of Allergy and Clinical Immunology for food allergy skin tests but were not tested for fenugreek because they had an inconclusive history will be excluded.

OTHER INFORMATION

Processing of personal and health data

The personal, clinical and photographic data of the patients involved in the study will be processed in compliance with current regulations on privacy protection, according to the normal procedures already in place in the A.O.U. "G. Martino" of Messina.

In addition, the patients, by means of special forms, duly filled out and signed, have given their consent to the processing of clinical data, including photographic or filmed images related to the health care services being processed anonymously for the purposes of clinical research, epidemiology, training and studies of pathologies.

Costs

No cost burden will be caused by the study to the National Health Service or to the A.O.U. "G. Martino" as no additional or different examinations from normal clinical practice are expected.

Statistical analysis

A descriptive analysis of the demographic and clinical characteristics of the subjects involved in the study will be performed. Categorical variables related to fenugreek-positive subjects and any other co-sensitizing allergens will be expressed as absolute and/or relative frequencies.

Bibliography

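### The cross-reactivity aim rests on co-sensitization frequencies in fenugreek-positive patients alone, although fenugreek-negative patients are eligible and could supply a reference level

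*Combined protocol and SAP*

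**What the plan says.** All references are to the combined protocol and SAP.

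- **Purpose of the study:** one aim is "to highlight possible cross-reactivity between fenugreek and other legumes or other foods".
- **Possible benefits:** a finding of relevant allergenicity "could prompt further study of molecular allergens useful for highlighting new patterns of cross-reactivity".
- **Clinical Case History:** the patients were seen "on an outpatient visit during the period from January 2022 to December 2023 to perform skin prick tests for foods".
- **Inclusion criteria:** adults who attended "for suspected allergic reaction after ingestion of spicy foods or intake of phytotherapeutic products containing fenugreek and were prick-by-prick tested with fenugreek". No positive result is required. The exclusion criteria remove minors and patients who were not tested with fenugreek because their history was inconclusive. They do not remove patients who tested negative.
- **Statistical analysis:** there are two sentences. The first is "A descriptive analysis of the demographic and clinical characteristics of the subjects involved in the study will be performed". The second is "Categorical variables related to fenugreek-positive subjects and any other co-sensitizing allergens will be expressed as absolute and/or relative frequencies".
- **Costs:** "no additional or different examinations from normal clinical practice are expected". The food tests are therefore those of routine care, and no panel is listed.

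**The concern.** A co-sensitization percentage in fenugreek-positive patients mixes two things: how often patients of this clinic react to that food anyway, and any excess that goes with fenugreek sensitization. Only the second bears on cross-reactivity. Without the same percentage in comparable fenugreek-negative patients, the two cannot be separated. The foods listed most often may simply be those that are commonly positive, or commonly tested, in this clinic.

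The study hopes to prompt molecular work on patterns of cross-reactivity, so readers need to see which foods stand out from background. A second gap makes this worse. Testing follows routine practice, and the plan does not say whether the denominator for a food is all fenugreek-positive patients or only those tested with that food.

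**Working it through.** The documents give no sample size, rate or expected frequency, so there is no figure to reproduce. The check is a reading of the text followed by illustrations. **Every count and rate below is assumed.**

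**1. Reading.** Fenugreek-negative patients are eligible because the entry condition is testing and not its result. The goal under Possible benefits, estimating how often sensitization occurs among patients with a suggestive history, also needs them in the denominator. Neither sentence of the Statistical analysis section names a split by fenugreek result, a measure of association, an interval or a denominator per food.

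**2. Background alone.** With 5 legumes, each independently positive with probability b, the chance of at least one legume co-sensitization is 1 − (1 − b)^5:

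- b = 0.10: 1 − 0.90^5 = 41%
- b = 0.20: 1 − 0.80^5 = 67%
- b = 0.30: 1 − 0.70^5 = 83%

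These arise with no cross-reactivity at all.

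**3. Same planned output, different meaning.** Take 10/20 fenugreek-positive patients reacting to a legume (50%, Wilson 95% CI 30% to 70%) and 40 negatives tested with the same legume.

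| Negatives reacting | Difference (Newcombe 95% CI) | Odds ratio |
|---|---|---|
| 4/40 (10%) | +40 points (16 to 61) | (10×36)/(10×4) = 9.0 |
| 12/40 (30%) | +20 points (−5 to 43) | (10×28)/(10×12) = 2.3 |
| 20/40 (50%) | 0 points (−25 to 25) | (10×20)/(10×20) = 1.0 |

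With fewer positives, take 4/10 (40%, exact 95% CI 12% to 74%):

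- Against 12/40: OR (4×28)/(6×12) = 1.6, exact 95% CI 0.27 to 8.0.
- Against 2/40: OR (4×38)/(6×2) = 12.7, exact 95% CI 1.4 to 156.

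The two intervals overlap widely, so at such counts the comparison is descriptive.

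**4. What a crude comparison cannot show.** Let half the cohort be highly atopic. Let fenugreek positivity be 30% v 5% and legume positivity 40% v 10% (high v low atopy), independent within each half.

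- Fenugreek-positive overall: 0.5×0.30 + 0.5×0.05 = 0.175.
- Share highly atopic: 0.15/0.175 = 0.857 in positives and 0.35/0.825 = 0.424 in negatives.
- Legume positivity: 0.857×0.40 + 0.143×0.10 = 0.357 in positives and 0.424×0.40 + 0.576×0.10 = 0.227 in negatives. OR 1.9 with no cross-reactivity.
- An unrelated food at 30% v 8% by atopy: 0.269 v 0.173, OR 1.75.
- Now let shared allergens turn a fraction k of the remaining legume-negative fenugreek-positives positive: 1 − (1 − 0.357)(1 − k). For k = 0.2 this is 0.486, OR 3.2. For k = 0.4 it is 0.614, OR 5.4. The unrelated food stays at 1.75.

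The contrast between legumes and unrelated foods therefore carries information that the crude odds ratio lacks.

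**5. Several foods.** With no true difference and independent foods, the chance that at least one 95% interval excludes 1 is at most 1 − 0.95^5 = 23% for 5 foods and 1 − 0.95^10 = 40% for 10.

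**6. Denominator.** If 6 of 10 fenugreek-positive patients were tested with a food and 3 reacted, the figure is 3/6 = 50% or 3/10 = 30%. The plan does not say which.

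**The case against.** The strongest reply is that the study is descriptive and aims only to highlight possibilities. Listing the foods that co-sensitize in positive patients is a coherent way to name candidates, and the protocol poses no comparative question. The first analysis sentence also covers all subjects, and other skin-test results could count as clinical characteristics, so a split by result is unmentioned but not ruled out. The documents do not say how many negatives there are or whether they had the same tests, and clinicians may have tested more legumes after a positive fenugreek result.

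The comparison could also mislead or be too weak. With 10 positives, 40 negatives and the rates of step 4 of the working, a Fisher exact test gives p < 0.05 about 12% of the time from atopy alone, 33% with k = 0.2 and 59% with k = 0.4.

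Much of this stands as a limit on what the comparison can show. The estimates would be imprecise, atopy confounds them, selective testing is not removed by restricting denominators, and the benefit depends on what the charts contain. It does not remove the gap. Naming candidates still requires knowing which foods exceed background. A general sentence on characteristics that mentions neither co-sensitization nor the fenugreek result specifies no reference level. The remedy is itself descriptive and asks for no powered test.

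**Conclusion.** The concern holds and should be fixed before analysis. Followed as written, the plan yields a percentage that fits anything from no association to a strong one: odds ratios of 1.0 to 9.0 for the same 10/20 in the illustration. That the reference level is missing follows directly from the text. How far this would distort the actual results is unknown, because all counts and rates used here are assumed. A comparison with fenugreek-negatives would give an internal reference from a selected group with suggestive histories. It would be neither a population rate nor proof of cross-reactivity.

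**What to change.** Add to the Statistical analysis section:

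- For each legume or other food, report positive/tested separately in fenugreek-positive and fenugreek-negative included patients. Use as denominator only those tested with that food, and show the number tested in each group so that selective testing is visible.
- Give the risk difference or odds ratio with an exact 95% CI, as description and without confirmatory claims.
- Show unrelated foods or allergens beside the legumes. A similar excess in both points to general atopy rather than shared allergens.
- Report skin-test overlap as co-sensitization, and state that any excess over fenugreek-negatives is hypothesis-generating.
- If negatives are few, or were not tested with the same foods, limit the conclusion to co-sensitization.

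The cost is two or three sentences and one extra table, with no new patients or tests, provided the charts hold comparable food tests for the negatives. The price is wide intervals when positives are few, several foods compared at once, and remaining selection in who was tested with what.

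### Do the co-sensitization percentages need a stated base and a confidence interval before the analysis can go ahead?

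*Combined protocol and SAP*

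**What the plan says.** The *Statistical analysis* section has two sentences. The first is general: "A descriptive analysis of the demographic and clinical characteristics of the subjects involved in the study will be performed". The second covers the results of interest: "Categorical variables related to fenugreek-positive subjects and any other co-sensitizing allergens will be expressed as absolute and/or relative frequencies". No section mentions a confidence interval, a hypothesis test, a sample size or a precision target.

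Other sections bear on the denominators:

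- *Inclusion criteria*: patients qualify if, among other things, they "were prick-by-prick tested with fenugreek, will be included". No test with any other food is required.
- *Costs*: "no additional or different examinations from normal clinical practice are expected". The other food tests are therefore those done in routine care, and no fixed panel is listed.
- *Purpose of the study*: besides reviewing histories, the aim is "to highlight possible cross-reactivity between fenugreek and other legumes or other foods".
- *Possible benefits*: "To assess the true incidence of sensitization to fenugreek in the population with clinical history indicative of allergy to spices or nutraceuticals".
- *Exclusion criteria*: patients who "were not tested for fenugreek because they had an inconclusive history will be excluded".

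**The concern.** Two things appear to be missing.

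**The base for each co-sensitizing food.** The base for fenugreek positivity is clear, since every included patient was tested with fenugreek. For a second food it is not. If routine testing varied, some fenugreek-positive patients have no result for that food. Counting them as negative gives one percentage and leaving them out gives another. With no rule in the plan, the choice would be made after the data are in hand, for the figure closest to the cross-reactivity purpose.

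**Precision.** A bare percentage from a small subgroup tells the reader little about its uncertainty. The *Possible benefits* section also speaks of an incidence in a population, which sounds like an inferential aim. The wording in *Statistical analysis* would even allow a percentage to be printed without its count.

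At stake is how a reader interprets the co-sensitization figures. No test, threshold or decision depends on them.

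**Working it through.** The document gives no patient count, expected rate or precision target, so there is no figure to reproduce. All counts below are assumptions.

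**1. How far the base can move the percentage.** Let N be the fenugreek-positive patients, m those of them tested with a given food, and x those positive to it. The two candidate percentages are x/N and x/m, and their ratio is N/m. The exact (Clopper-Pearson) 95% interval for x out of n runs from the 2.5% quantile of Beta(x, n − x + 1) to the 97.5% quantile of Beta(x + 1, n − x).

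| Base (x = 6) | Percentage | Exact 95% interval |
|---|---|---|
| All 20 positives | 6/20 = 30% | 11.9% to 54.3% |
| 16 tested | 6/16 = 37.5% | 15.2% to 64.6% |
| 12 tested | 6/12 = 50% | 21.1% to 78.9% |
| 10 tested | 6/10 = 60% | 26.2% to 87.8% |

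If all 20 were tested, the two bases coincide. With 16 tested, the gap is 37.5 − 30 = 7.5 points. It reaches 30 points only if half the positives were never tested with that food. A second assumed case, 6 of 30, runs from 20.0% over all positives to 25.0%, 40.0% and 66.7% with 24, 15 and 9 tested.

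**2. Whether one base is the right one.** Let r be the positivity rate that the N − m untested patients would have shown. Had everyone been tested, the percentage would be

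(x + r(N − m))/N.

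- Setting r = 0 gives x/N, the all-positives figure.
- Setting r = x/m gives x/m, the tested-only figure.

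Each base is therefore an assumption about the untested patients. If foods were chosen because the history pointed to them, r would be expected to lie between 0 and x/m, and the full-panel figure would lie between the two percentages. Take N = 20, m = 10, x = 6, and suppose 1 of the 10 untested would have been positive (r = 0.1). Then (6 + 1)/20 = 35%, which is nearer to 30% than to 60%. A tested-only rule would not reliably improve the figure.

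**3. What an interval adds.** The formula in step 1 needs only x and n. For an assumed 20% fenugreek-positive, the exact interval is 10.0% to 33.7% at 10/50, 12.7% to 29.2% at 20/100 and 16.6% to 23.8% at 100/500. Any reader given the count and its base can obtain these. The interval covers sampling error only and says nothing about who was referred or selected for testing.

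**4. The incidence wording.** The *Possible benefits* sentence limits its population to patients with an indicative history. The *Exclusion criteria* remove those who went untested because their history was inconclusive. The two largely agree, so that exclusion does not undermine the stated target. The word incidence is loose for another reason: a single test result in a one-clinic referral series gives a proportion sensitized. That is a slip of terminology, and correcting it would alter no table.

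**The case for a change.** The strongest case for a change is that it would be cheap and that the affected figure matters. A couple of sentences fixing the base, with an interval for each proportion, would cost nothing in patients or tests and would remove a choice otherwise made with the results in view. If untested patients are counted as negative, the error in the observed percentage runs one way, towards too little co-sensitization. Nothing in the document shows that all patients had the same panel.

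Part of this stands. The plan does leave the handling of untested patients open, and a percentage printed without its count and base would be hard to interpret. A percentage among fenugreek-positives alone also shows co-sensitization and does not by itself establish cross-reactivity.

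It falls short of requiring an amendment. The problem depends on varied panels, which the document does not report. Fixing the tested-only base would replace a possible understatement with a possible overstatement. Intervals on a selected series may also suggest more inferential weight than it can bear. The records cover January 2022 to December 2023 and the document is dated January 15, 2024, so only reporting is affected.

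**Conclusion.** No change to the plan is needed. The omissions are real: no interval is planned, and the base for each co-sensitizing food is not defined. The first is a reporting addition that corrects no result. The second is a detail that analysts fill sensibly when they lay out the tables, by giving for each food the numbers positive, tested and not tested among fenugreek-positive patients. Both percentages can then be read off, and the choice of base hides nothing.

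The size of the effect is unknown, because the document gives no counts. Under the assumed 20 fenugreek-positives with 6 positive to one food, it runs from nothing (a common panel), through 7.5 points (16 tested), to 30 points (10 tested). The conclusion rests on the study staying descriptive, with no test or decision rule tied to these percentages. It would be weaker if they were printed without counts and the panels were found to differ widely.
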